6. COLLECTION OF STUDY VARIABLES

The schedule for assessments at Screening and during the Treatment Period is presented in [Table 1](#). The schedule of study procedures during follow-up for patients who have completed MEDI4736 treatment and achieved disease control (until confirmed PD) and patients who have discontinued MEDI4736 due to toxicity in the absence of confirmed PD is presented in [Table 2](#). The schedule of study procedures during follow-up for patients who have discontinued MEDI4736 treatment due to confirmed PD is presented in [Table 3](#).

6.1 Recording of data

The InForm Web-Based Data Capture system will be used for data collection and query handling. The investigator will ensure that data are recorded on the eCRFs as specified in the study protocol and in accordance with the instructions provided.

The investigator ensures the accuracy, completeness, legibility and timeliness of the data recorded and of the provision of answers to data queries according to the Clinical Study Agreement. The investigator will sign the completed eCRFs. A copy of the completed eCRFs will be archived at the study site.

6.2 Data collection at enrolment and follow-up

6.2.1 Enrolment procedures

The following assessments and procedures should be performed within 42 days prior to the first dose of MEDI4736 ([Table 1](#)). For details of the nature of the assessments, see below.

- Signed informed consent for the study and assignment of a patient identification number
 - Preliminary eligibility criteria (investigator's opinion)
 - Demographic details including age, sex and ethnicity and also tobacco and alcohol consumption history
 - Details on previous treatments for NSCLC
 - A mandatory provision of a recent (≤ 3 months) tumour biopsy taken following the completion of the most recent systemic anti-cancer therapy, except if technically not feasible and after discussion with the study physician (for collection and processing procedures, refer to Section 6.6.1 and the Laboratory Manual). Tumour lesions planned for biopsy must not be used as index lesions for assessment of disease
- AND

- Provision of an archived tumour tissue block (or at least 10 newly cut unstained slides) where such samples exist in a quantity sufficient to allow for analysis (refer to Section 6.6.1 and the Laboratory Manual for details).

The following assessments and procedures should be performed within 28 days prior to the first dose of MEDI4736 (Table 1). For details of the nature of the assessments, see below.

- Formal eligibility criteria verification
- Past medical and surgical history
- Details of any palliative radiotherapy
- Physical examination to assess all conditions that are current and ongoing
- Weight and vital signs: body temperature, respiratory rate, pulse, systolic and diastolic blood pressure (BP) and oxygen saturation
- Recording of AEs from the time of consent
- Concomitant medications
- WHO performance status
- Haematology, clinical chemistry and urinalysis
- Coagulation tests: prothrombin time, activated partial thromboplastin time (APTT) and international normalised ratio (INR).
- Hepatitis B and C testing as per local practice
- HIV-1 antibody
- Thyroid function tests: triiodothyronine (T3; free [if available]), total thyroxine (T4 [or T4 free]), and thyroid stimulating hormone (TSH).
- Pregnancy testing for female patients, as clinically indicated (urine human chorionic gonadotropin [hCG] or serum β hCG)
- 12-lead ECG recording
- Blood samples for the analysis of biomarkers (including those for circulating soluble factors, messenger RNA/micro RNA and soluble PD-L1; see Section 6.6).
- A sample for PGx (DNA) analysis (optional).

- Tumour assessment scans of the chest and abdomen (including liver and adrenal glands) for assessment of disease by CT/MRI (see [Appendix F](#)).

The Principal Investigator/sub-investigator should adhere to the study plan, procedures and perform tests/observations in accordance with the protocol.

6.2.2 Follow-up procedures and survival follow-up

Patients should be discontinued from MEDI4736 if any discontinuation criteria are fulfilled, see Section [5.8](#). The assessments to be carried out during follow-up are detailed in [Table 2](#) (for patients achieving disease control or who are discontinued due to toxicity in the absence of confirmed PD) and [Table 3](#) (for patients discontinuing due to confirmed PD).

Any serious and/or non-serious AEs ongoing at the time of treatment discontinuation or which have occurred during the follow-up period must be followed-up (in accordance with Section [6.4.3](#) and Section [6.4.4](#)). Appropriate safety evaluations should be repeated and/or additional tests performed at any time when clinically indicated, or at the discretion of the investigator, until resolution, unless, in the investigator's opinion, the condition is unlikely to resolve due to the patient's underlying disease. If the patient is lost to follow-up, then this should be noted in the eCRF.

Survival follow-up

Assessments for survival status should be made following confirmed objective disease progression (per RECIST v1.1 criteria) as presented in [Table 2](#) (for patients achieving disease control or who are discontinued due to toxicity in the absence of confirmed PD) and [Table 3](#) (patients discontinuing due to confirmed PD).

Survival information may be obtained via telephone contact with the patient, patient's family or by contact with the patient's current physician.

In addition, patients should be contacted in the week following the data cut-off for the final analysis of OS, which will take place 12 months after the last patient is enrolled in each cohort, to provide complete survival data.

The status of patients ongoing in the study, those withdrawn (from the study) and those lost to follow-up at the time of an OS analysis should be obtained by the site personnel, by checking the patient notes, hospital records, contacting the patient's general practitioner and checking publicly available death registries. In the event that the patient has actively withdrawn consent to the processing of their personal data, the vital status of the patient (ie, if the patient is dead or alive) can be obtained by site personnel from publicly available resources where it is possible to do so under applicable local laws.

6.3 Efficacy

6.3.1 Method of assessment using RECIST 1.1 criteria

RECIST 1.1 criteria will be used to assess patient response to treatment by determining ORR, DoR, DCR, TTR and PFS. The RECIST 1.1 guidelines for measurable, non-measurable, target and non-target lesions and the objective tumour response criteria (CR, PR, SD or PD) are presented in [Appendix F](#).

The methods of assessment of tumour burden used at baseline CT/MRI scans of the chest and abdomen (including liver and adrenal glands) must be used at each subsequent follow-up assessment.

The baseline assessment should be performed no more than 28 days before the start of MEDI4736 treatment and ideally as close as possible to the start of investigational product. Efficacy for all patients will be assessed by objective tumour assessments every 8 weeks for the first 48 weeks (relative to the date of the first MEDI4736 infusion; [Table 1](#)), then every 12 weeks thereafter until confirmed objective disease progression as defined by RECIST 1.1 (irrespective of the reason for stopping treatment/or subsequent therapy). If an unscheduled assessment is performed, and the patient has not progressed, every attempt should be made to perform the subsequent assessments at their scheduled visits.

For patients who discontinue MEDI4736 due to toxicity in the absence of confirmed objective progression objective tumour assessments should be continued every 8 weeks for 48 weeks (relative to the date of the first MEDI4736 infusion) then every 12 weeks until confirmed objective disease progression.

Disease progression requires confirmation, the confirmatory scan should occur preferably at the next scheduled visit and no earlier than 4 weeks after the initial assessment of PD in the absence of clinically significant deterioration. Treatment with MEDI4736 will continue between the initial assessment of progression and confirmation for progression. For all patients who are treated through progression and for patients who achieve disease control (ie, CR, PR or SD) at 12 months and restart study treatment upon evidence of PD (according to RECIST 1.1), with or without confirmation, during follow-up, the investigator should ensure patients do not have any significant, unacceptable or irreversible toxicities that indicate continuing or restarting treatment would not further benefit the patient. The patient must continue to meet those inclusion and exclusion criteria including re-consenting to continue or restart treatment as specified in [Section 4.3](#). Patients with rapid tumour progression or with symptomatic progression that requires urgent medical intervention (eg, central nervous system metastasis, respiratory failure due to tumour compression, spinal cord compression) will not be eligible to continue to receive study drug.

Progression would be considered confirmed if the following criteria are met:

- $\geq 20\%$ increase in the sum diameters of target lesions compared with the nadir at 2 consecutive visits (with an absolute increase of at least 5 mm)
- and/or significant progression (worsening) of non-target lesions or new lesions at the confirmatory PD time-point compared with the first time point where progression of non-target lesions or new lesions identified
- and/or additional new unequivocal lesions at the confirmatory PD time-point compared with the first time point new lesions identified.

In the absence of clinically significant deterioration the investigator should continue study treatment until progression is confirmed.

If progression is not confirmed then the patient should continue on study treatment and on treatment assessments.

If a patient discontinues treatment (and/or receives a subsequent cancer therapy) prior to progression then the patient should still continue to be followed until confirmed objective disease progression.

Categorisation of objective tumour response assessment will be based on the RECIST 1.1 criteria of response: CR, PR, SD and PD. Target lesion progression will be calculated in comparison to when the tumour burden was at a minimum (ie, smallest sum of diameters previously recorded on study). In the absence of progression, tumour response (CR, PR) and SD will be calculated in comparison to the baseline tumour measurements obtained before starting treatment.

Objective tumour response (CR or PR) should be confirmed preferably at the next scheduled visit and not less than 4 weeks after the visit when the response was first observed.

If the investigator is in doubt as to whether progression has occurred, particularly with response to non-target lesion or the appearance of a new lesion, it is advisable to continue treatment until the next scheduled assessment or sooner if clinically indicated and reassess the patient's status. If repeat scans confirm progression, then the date of the initial scan should be declared as the date of progression.

To achieve 'unequivocal progression' on the basis of non-target disease, there must be an overall level of substantial worsening in non-target disease such that, even in presence of SD or PR in target disease, the overall tumour burden has increased sufficiently to merit discontinuation of therapy. A modest 'increase' in the size of one or more non-target lesions is usually not sufficient to qualify for unequivocal progression status.

Following confirmed progression, patients should continue to be followed up for survival every 2 months as outlined in the study plan (Table 3). An exception are patients with

confirmed PD that continue to receive MEDI4736 at the discretion of the investigator (after consultation with the sponsor); these patients can receive treatment for a maximum of 12 months and will have scans every 8 weeks (relative to the date of the first infusion per [Table 1](#)) until study treatment is stopped.

Study drug should be discontinued if there is confirmed PD following a previous response (PR or CR) to study drug.

Patients with confirmed PD that discontinue MEDI4736, should have scans conducted according to local practice and submitted for ICR until the patient commences a new treatment (these scans are optional; see [Table 3](#)).

Patients who achieve and maintain disease control (ie, CR, PR, or SD) through to the end of the 12-month MEDI4736 treatment period may restart treatment with MEDI4736 upon evidence of PD, with or without confirmation, during follow-up. To restart treatment the patient must not have received an intervening systemic anti-cancer therapy post-MEDI4736 discontinuation. Patients who restart MEDI4736 must have a baseline tumour assessment within 28 days of restarting treatment with MEDI4736, all further scans should occur every 8 weeks (relative to the date of restarting treatment) until study treatment is stopped (maximum of 12 months of further treatment).

It is important to follow the assessment schedule as closely as possible. Please refer to the study plans ([Table 1](#) [Screening and the Treatment Period], [Table 2](#) [for follow-up of patients achieving disease control or who are discontinued due to toxicity in the absence of confirmed PD] and [Table 3](#) [for follow-up of patients discontinuing due to confirmed PD]) and [Appendix F](#).

6.3.2 Central reading of scans

An ICR of all scans used in the assessment of tumours using RECIST 1.1 modified for confirmation of progression and irRC ([Wolchok et al 2009](#), [Nishino et al 2013](#), see Section 11.1.2) will be conducted (see Section 12.2.1 for the analysis methods). All imaging assessments including unscheduled visit scans will be collected on an ongoing basis and sent to an AstraZeneca appointed Contract Research Organisation for central analysis. Results of these independent reviews will not be communicated to investigators, and the management of patients will be based solely upon the results of the RECIST assessment conducted by the investigator.

6.4 Safety

The Principal Investigator is responsible for ensuring that all staff involved in the study is familiar with the content of this section.

6.4.1 Definition of adverse events

An AE is the development of an undesirable medical condition or the deterioration of a pre-existing medical condition following or during exposure to a pharmaceutical product,

whether or not considered causally related to the product. An undesirable medical condition can be symptoms (eg, nausea, chest pain), signs (eg, tachycardia, enlarged liver) or the abnormal results of an investigation (eg, laboratory findings, ECG). In clinical studies, an AE can include an undesirable medical condition occurring at any time, including run-in or washout periods, even if no study treatment has been administered.

The term AE is used to include both SAEs and non-serious AEs.

For cases where it could be suspected that a tissue-derived medicine has been contaminated by a pathogen, information about any of the above conditions (including infection) should be collected. Any deterioration of the disease targeted in the study and associated symptoms should not be regarded as an AE as far as the deterioration can be anticipated.

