- Not protocol related: The event is related to an aetiology other than the procedure/intervention that was described in the protocol (the alternative aetiology must be documented in the study patient's medical record).

Adverse events based on signs and symptoms

All AEs spontaneously reported by the patient or reported in response to the open question from the study personnel: 'Have you had any health problems since the previous visit/you were last asked?', or revealed by observation will be collected and recorded in the eCRF. When collecting AEs, the recording of diagnoses is preferred (when possible) to recording a list of signs and symptoms. However, if a diagnosis is known and there are other signs or symptoms that are not generally part of the diagnosis, the diagnosis and each sign or symptom will be recorded separately.

Adverse events based on examinations and tests

The results from protocol mandated laboratory tests and vital signs will be summarised in the CSR. Deterioration as compared to baseline in protocol-mandated laboratory values and vital signs should therefore only be reported as AEs if they fulfil any of the SAE criteria or are the reason for discontinuation of treatment with the investigational product. An abnormal laboratory finding (including ECG findings) that requires an action or intervention by the investigator, or a finding judged by the investigator to represent a change beyond the range of normal physiologic fluctuation, should also be reported as an AE.

If deterioration in a laboratory value/vital sign is associated with clinical signs and symptoms, the sign or symptom will be reported as an AE and the associated laboratory result/vital sign will be considered as additional information. Wherever possible the reporting investigator uses the clinical, rather than the laboratory term (eg, anaemia versus low haemoglobin value). In the absence of clinical signs or symptoms, clinically relevant deteriorations in non-mandated parameters should be reported as AE(s).

Asymptomatic Grade 3 or 4 increases in amylase or lipase resulting in interruption of dosing (see Toxicity Guidelines - [Appendix G](#)) should be reported as AEs.

Deterioration of a laboratory value, which is unequivocally due to disease progression, should not be reported as an AE/SAE.

Any new or aggravated clinically relevant abnormal medical finding at a physical examination as compared with the baseline assessment will be reported as an AE.

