NB. Cases where a patient shows an AST **or** ALT ≥ 3 x ULN **or** total bilirubin ≥ 2 x ULN may need to be reported as SAEs. These cases should be reported as SAEs if after evaluation they meet the criteria for a Hy's Law case or if any of the individual liver test parameters fulfil any of the SAE criteria. For potential Hy's Law and Hy's Law to be met, the elevation in transaminases must precede or be coincident with (ie, on the same day) the elevation in total bilirubin, but there is no specified timeframe within which the elevations in transaminases and total bilirubin must occur.

Please refer to [Appendix E](#) 'Actions required in cases of combined increase of Aminotransferase and Total Bilirubin – Hy's Law', for further instructions in cases of combined increases of aminotransferase and total bilirubin.

Criteria for Hy's Law (FDA Guidance 2009)

- The drug causes hepatocellular injury, generally shown by a higher incidence of 3-fold or greater elevations above the ULN of ALT or AST than the (non-hepatotoxic) control drug or placebo
- Among trial subjects showing such aminotransferase elevations, often with aminotransferases much greater than 3 x ULN, one or more also show elevation of serum total bilirubin to >2 x ULN, without initial findings of cholestasis (elevated serum alkaline phosphatase)
- No other reason can be found to explain the combination of increased aminotransferases and total bilirubin, such as viral hepatitis A, B, or C; pre-existing or acute liver disease; or another drug capable of causing the observed injury.

Guidelines for management of patients with hepatic function abnormality are outlined in [Appendix G](#).

Disease progression

Disease progression can be considered as a worsening of a patient's condition attributable to the disease for which the investigational product is being studied. It may be an increase in the severity of the disease under study and/or increases in the symptoms of the disease. The development of new, or progression of existing metastasis to the primary cancer under study should be considered as disease progression and not an AE. Events, which are unequivocally due to disease progression, should not be reported as an AE during the study.

New cancers

The development of a new cancer should be regarded as an SAE. New primary cancers are those that are not the primary reason for the administration of the investigational product and have been identified after the patient's inclusion in this study.

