Deaths

All deaths that occur during the study, or within the protocol-defined follow-up period after the administration of the last dose of investigational product, must be reported as follows:

- Death clearly the result of disease progression should be reported to the study monitor at the next monitoring visit and should be documented in the eCRF but should not be reported as a SAE.
- Where death is not due (or not clearly due) to PD under study, the AE causing the death must be reported to the study monitor as a SAE within 24 hours. The report should contain a comment regarding the co-involvement of PD, if appropriate, and should assign main and contributory causes of death.
- Deaths with an unknown cause should always be reported as a SAE. A post mortem may be helpful in the assessment of the cause of death, and if performed a copy of the post-mortem results should be forwarded to AstraZeneca/MedImmune Drug Safety or its representative within the usual timeframes.

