12.2.7 Safety data

Safety and tolerability data will be presented for each cohort using the safety population.

AEs (both in terms of MedDRA preferred terms and CTCAE grade) will be listed individually by patient. The number of patients experiencing each AE will be summarised by CTCAE grade for each cohort.

Other safety data will be assessed in terms of physical examination, clinical chemistry, haematology, vital signs and ECGs. Exposure to MEDI4736 will be summarised. Time on study and MEDI4736 dose delays will also be summarised. At the end of the study, appropriate summaries of all safety data will be produced, as defined in the SAP.

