	Grade of the Event (NCI CTCAE version 4.03)	Dose Modifications	Toxicity Management
Pneumonitis/ILD	Grade of Pneumonitis (CTCAE version 4.03)	Any Grade	
 - Monitor patients for signs and symptoms of pneumonitis or ILD (new onset or worsening shortness of breath or cough). Patients should be evaluated with imaging and pulmonary function tests including other diagnostic procedures as described below - Initial work-up may include clinical evaluation, monitoring of oxygenation via pulse oximetry (resting and exertion), laboratory work-up and high-resolution CT scan.
	Grade 1 (Asymptomatic, clinical or diagnostic observations only, intervention not indicated)	No dose modification required. However, consider holding study drug/study regimen dosing as clinically appropriate and during diagnostic work-up for other etiologies	For Grade 1 (Radiographic Changes Only) 
 - Monitor and closely follow up in 2-4 days for clinical symptoms, pulse oximetry (resting and exertion) and laboratory work-up and then as clinically indicated - Consider pulmonary and infectious disease consult
	Grade 2 (Symptomatic, medical intervention indicated, limiting instrumental ADL)	Hold study drug/study regimen dose until grade 2 resolution to \leq Grade 1 
 • If toxicity worsens then treat as Grade 3 or Grade 4 • If toxicity improves to baseline 	For Grade 2 (Mild to Moderate New Symptoms) 
 - Monitor symptoms daily and consider hospitalization - Promptly start systemic steroids (e.g., prednisone 1-2mg/kg/day or IV equivalent) - Reimaging as clinically indicated

Dosing Modification and Toxicity Management Guidelines for Immune-mediated, Infusion Related, and Non Immune-mediated Reactions (MEDI4736 Monotherapy or Combination therapy with Tremelimumab or Tremelimumab monotherapy)

	Grade of the Event (NCI CTCAE version 4.03)	Dose Modifications	Toxicity Management

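### Sections 6.4.1 and 6.4.3 use different tests, foreseeability and certainty of cause, to decide when disease worsening is not an adverse event, and the protocol does not say which governs

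*Protocol*

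**What the plan says.** Section 6.4.1 defines an AE broadly and without regard to causality. Its last sentence then removes worsening of the disease under study, adding that "associated symptoms should not be regarded as an AE as far as the deterioration can be anticipated".

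Section 6.4.3 returns to the subject under several subheadings:

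- **Disease progression.** Progression is described so as to include symptoms: "It may be an increase in the severity of the disease under study and/or increases in the symptoms of the disease". The exemption then reads: "Events, which are unequivocally due to disease progression, should not be reported as an AE during the study". New or worsening metastases are exempted separately and without that qualifier: "progression of existing metastasis to the primary cancer under study should be considered as disease progression and not an AE".
- **Examinations and tests.** The same standard is repeated: "Deterioration of a laboratory value, which is unequivocally due to disease progression, should not be reported as an AE/SAE".
- **Deaths.** "Where death is not due (or not clearly due) to PD under study, the AE causing the death must be reported", and deaths of unknown cause are always reported as SAEs.

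Section 6.4.2 defines an SAE as an AE that meets at least one seriousness criterion. Section 12.2.7 gives the output that depends on all this: "The number of patients experiencing each AE will be summarised by CTCAE grade for each cohort".

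**The concern.** The two sections govern the same events, because Section 6.4.3 counts increased symptoms as progression and Section 6.4.1 covers symptoms associated with the disease. Yet one turns on whether the deterioration could be foreseen and the other on whether its cause is certain. In patients with advanced lung cancer after at least two prior regimens, worsening dyspnoea, cough, fatigue or pain can often be foreseen while its cause in a given patient is unclear. Appendix G names overlapping symptoms as signals of an immune toxicity: "Monitor patients for signs and symptoms of pneumonitis or ILD (new onset or worsening shortness of breath or cough".

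Safety is a secondary objective for all cohorts. There is no control arm in which a recording difference would cancel, no data monitoring committee (Section 12.4), and no safety hypothesis is tested (Section 12.2). AE frequencies are read at face value, so what counts as an AE should be fixed in one way. An event that falls outside the AE definition also falls outside the SAE definition, and therefore outside the 24-hour SAE reporting in Section 6.4.4.

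**Working it through.** The protocol states no figure that could be reproduced on this point. The check is a comparison of the two exclusion tests as they apply to symptoms and clinical events.

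**Inputs**

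- Test A (Section 6.4.1): target-disease deterioration and associated symptoms are not an AE if the deterioration can be anticipated.
- Test B (Section 6.4.3, Disease progression): an event is not reported if it is unequivocally due to progression.

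**Crossing the tests**

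| Anticipated? | Unequivocally due to progression? | Test A | Test B | Agree? |
|---|---|---|---|---|
| Yes | Yes | Not an AE | Not an AE | Yes |
| Yes | No | Can be read as not an AE | Record | No |
| No | Yes | AE | Not reported | No |
| No | No | AE | Record | Yes |

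The tests can disagree in two of four cells. In the second row the disagreement depends on how Section 6.4.1 is read. In the third it follows directly from the wording.

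**Position of the other rules.** The laboratory rule uses Test B's word. The death rule requires reporting when attribution to progression is not clear, which amounts to the same standard. The metastasis exemption is a separate category with no certainty qualifier, so Section 6.4.3 does not rest on one test alone, but for symptoms such as dyspnoea or fatigue the operative word is the certainty one. Section 6.4.1 is the outlier.

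**Size.** The effect on a reported rate would be: rate under Test A = rate under Test B × (1 − share of those events that are anticipated but not unequivocal), leaving aside the third row, which works the other way. The protocol gives no such share. Purely to show the scale, take the Grade 3 or higher dyspnoea rate of 5.1% that Section 1.1.3.2 reports for Study 1108, and assume shares of 0%, 25% and 50%:

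- 5.1% × 1.00 = 5.1%
- 5.1% × 0.75 = 3.8%
- 5.1% × 0.50 = 2.6%

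The shares are assumptions, and Study 1108 enrolled advanced solid tumours generally. This is not an estimate for the present trial.

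**The case against.** The best reply is that Section 6.4.1 already presupposes attribution: what it removes is deterioration of the target disease and its symptoms, so dyspnoea of unknown origin has not yet qualified. Section 6.4.3 would then supply the degree of certainty needed, and the two would form one rule. This is a sensible reading and it weakens the conflict in the second row of the table. But the protocol does not state it, and it leaves the third row unresolved, since unequivocal progression that nobody anticipated is an AE under one section and not reportable under the other.

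A reader might infer that early pneumonitis will go unrecorded. The documents do not support that. Section 5.5.3.1 lists pneumonitis as an event of special interest, asks that neoplastic causes of a suspected immune event be ruled out, and refers doubts to the study physician. Section 6.4.3 collects events by an open question and by observation. Appendix G treats events without a clear alternative cause as potentially immune related and calls for imaging and lung function tests. These provisions limit the loss without settling which AE test applies. Likewise, fatal cases of doubtful cause are protected by the death rule.

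A reader might also infer that sites will record differently. The wording permits this, but nothing in the protocol shows that it happens.

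Finally, a reader might try to size the effect from Study 1108. Grade 3 or higher events occurred in 141 of 393 patients (35.9%). Dyspnoea (5.1%, about 20) plus fatigue, general health deterioration and back pain (2.3% each, about 9) gives 20 + 3 × 9 = 47, and (141 − 47)/393 = 23.9%. That range cannot be used. It subtracts patient-events from a count of patients, so it needs every such event to be in dispute, no patient to have two of them, and none to have any other Grade 3 or higher event. The same study had 229 SAEs in 123 patients, about 1.9 per affected patient, so multiple events were common. Its AE recording rules are not given either.

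**Conclusion.** The inconsistency is real. Section 6.4.1 excludes by foreseeability, Section 6.4.3 by certainty of cause, and the protocol does not say which prevails. They can part for anticipated events of doubtful attribution and for unanticipated but unequivocal progression. Through the SAE definition the ambiguity extends to non-fatal serious events.

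Its size cannot be determined from the protocol. The conclusion rests on the wording alone, and on the view that a descriptive single-arm safety summary needs a single counting rule. It does not bear on the objective response rate. It is an inexpensive correction that should be made, not evidence that safety signals will be missed.

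**What to change.** Reconcile the passages by replacing the last sentence of Section 6.4.1 with a cross-reference to the standard already in Section 6.4.3: only events unequivocally due to progression of the disease under study are not AEs, and events of uncertain attribution are recorded, whether or not they could be anticipated. The separate metastasis exemption can remain. The death rule needs no change, because it already resolves doubt in the same direction.

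The cost is one sentence and a reminder to sites. Somewhat more AEs will be recorded, and AE rates may look slightly less favourable.
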